# T16.1.9.18 Summary of Vital Signs (Safety Population)

Vital Signs	Visit	Statistic	Test(N = xxx)	Reference (N = xxx)	Placebo (N = xxx)
Systolic Blood Pressure (mmHg)	1	n	XXX	XXX	XXX
		$Mean \pm SD$	$xxx.x \pm xx.x$	$xxx.x \pm xx.x$	$xxx.x \pm xx.x$
		Median	XXX.X	XXX.X	XXX.X
		Range	XX.X – XX.X	XX.X - XX.X	XX.X – XX.X
	4/ET				
Diastolic Blood Pressure (mmHg) Pulse Rate (beats/min)					
Respiration Rate (breaths/min)					
Temperature (F)					
,	DI cont				
Test: Tazarotene Cream 0.05% (Foug Reference: TAZORAC ® (tazarotene)					
Placebo: Placebo (vehicle) Cream (F					

Path: L:\Studies\_Sas\_Codes\Clinical Trial

Created on: ddmmmyy hh:mm

## L16.2.1 Listing of Discontinued Subjects

Treatment	Subject	Discontinuation	
Group	Number	Reason	Population
Test	xx - xxxx	Withdrew Consent	Safety
	xx - xxxx	Lost to Follow-up	Safety

#### Reference

#### Placebo

Test: Tazarotene Cream 0.05% (Fougera Pharmaceuticals Inc.) Reference: TAZORAC® (tazarotene) Cream, 0.05% (Allergan, Inc.) Placebo: Placebo (vehicle) Cream (Fougera Pharmaceuticals Inc.)

Path: L:\Studies Sas Codes\Clinical Trial

Created on: ddmmmyy hh:mm

### L16.2.2 Listing of Protocol Deviations

Treatment	Subject		
Group	Number	Protocol Deviation Summary	Population
Test	xx - xxxx	Outside Visit Window	Safety

#### Reference

#### Placebo

Test: Tazarotene Cream 0.05% (Fougera Pharmaceuticals Inc.) Reference: TAZORAC® (tazarotene) Cream, 0.05% (Allergan, Inc.) Placebo: Placebo (vehicle) Cream (Fougera Pharmaceuticals Inc.)

Path: L:\Studies\_Sas\_Codes\Clinical Trial\\SAS\OUT

Created on: ddmmmyy hh:mm

# L16.2.3.1 Subjects Excluded from the Per-Protocol Population Data Set

Treatment Group	Subject Number	Exclusion Reason
Test	xx - xxxx	Subject did not meet IE criterion.
	XX - XXXX	Subject took prohibited medications

Reference

Placebo

Test: Tazarotene Cream 0.05% (Fougera Pharmaceuticals Inc.)
Reference: TAZORAC ® (tazarotene) Cream, 0.05% (Allergan, Inc.)
Placebo: Placebo (vehicle) Cream (Fougera Pharmaceuticals Inc.)

Path: L:\Studies\_Sas\_Codes\Clinical Trial

Created on: ddmmmyy hh:mm

# L16.2.3.2 Subjects Excluded from the Modified Intent-to-Treat Data Set

Treatment Subject Exclusion		Exclusion
Group Number		Reason
Test	xx - xxxx	Subject did not have at least one post-randomization evaluation
	XX - XXXX	Subject did not have at least one post-randomization evaluation

Reference

Placebo

Test: Tazarotene Cream 0.05% (Fougera Pharmaceuticals Inc Reference: TAZORAC ® (tazarotene) Cream, 0.05% (Allergan		
Placebo: Placebo (vehicle) Cream (Fougera Pharmaceuticals		
Path: L:\Studies_Sas_Codes\Clinical Trial\\SAS\OU	UT Created on: ddmmmyy hh:mm	Page 1 of N

# L16.2.4.1 Listing of Demographic Data

Treatment Group	Subject Number	Age	Sex	Ethnicity	Race
Test	xx - xxxx	30	Female	Not Hispanic or Latino	Black or African American

#### Reference

Placebo

Test: Tazarotene Cream 0.05% (Fougera Pharmaceuticals Inc.) Reference: TAZORAC® (tazarotene) Cream, 0.05% (Allergan, Inc.) Placebo: Placebo (vehicle) Cream (Fougera Pharmaceuticals Inc.)

Path: L:\Studies\_Sas\_Codes\Clinical Trial

Created on: ddmmmyy hh:mm

# L16.2.4.2 Listing of Medical History

Treatment	Subject					
Group	Number	Category	Reported Term	Onset Date	End Date	Ongoing
Test	xx - xxxx	Gynecologic	Menopause	2003	2003	

Reference

Placebo

Test: Tazarotene Cream 0.05% (Fougera Pharm Reference: TAZORAC ® (tazarotene) Cream, 0. Placebo: Placebo (vehicle) Cream (Fougera Ph	05% (Allergan, Inc.)		
Path: L:\Studies_Sas_Codes\Clinical Trial	\SAS\OUT	Created on: ddmmmyy hh:mm	Page 1 of N

## L16.2.4.3 Listing of Concomitant Medications

#### Test: Tazarotene Cream 0.05%

Subject	Medication/			Start/End			
Number	Therapy Name	Dosage	Frequency	Route	Date	Indication	
xx - xxxx	LISINOPRIL	20 MG	QD	РО	yyyy-mm-dd/	HYPERTENSION	

Note to programmer: table will continue for reference and placebo group

- Path: L:\Studies\_Sas\_Codes\Clinical Trial
- \SAS\OUT

Created on: ddmmmyy hh:mm

## L16.2.5.1 Listing of Visit Date Information

Treatment	Subject	Inform Consent				Visit 4 or
Group	roup Number Date		Visit 1	Visit 2	Visit 3	Early Termination
Test	xx - xxxx	yyyy-mm-dd	yyyy-mm-dd	yyyy-mm-dd	yyyy-mm-dd	yyyy-mm-dd

,	Test: Tazarotene Cream 0.05% (Fougera Pharmaceuticals Inc.)
]	Reference: TAZORAC ® (tazarotene) Cream, 0.05% (Allergan, Inc.)
]	Placebo: Placebo (vehicle) Cream (Fougera Pharmaceuticals Inc.)

Path: L:\Studies\_Sas\_Codes\Clinical Trial

\SAS\OUT

Created on: ddmmmyy hh:mm

# L16.2.5.2 Listing of Drug Administration

Treatment	Subject	Date of	Date of	Total Doses	Dosing
Group	Number	First Dose	Last Dose	Applied	Compliance (%)
Test	xx - xxxx	yyyy-mm-dd	yyyy-mm-dd	XX	XX.X

Reference

Placebo

Test: Tazarotene Cream 0.05% (Fougera Pharmaceuticals Inc.) Reference: TAZORAC® (tazarotene) Cream, 0.05% (Allergan, Inc.) Placebo: Placebo (vehicle) Cream (Fougera Pharmaceuticals Inc.)

Path: L:\Studies\_Sas\_Codes\Clinical Trial

Created on: ddmmmyy hh:mm

Treatment	Subject	U			Visit 4 or	Treatment	Treatment
Group	Number			Visit 3	Early Termination	Success*	Success**
Test	xx - xxxx	4	4	3	0	Yes	Yes
	xx - xxxx	4	4	3	2	Yes	No
	xx - xxxx	4	4	3	3	No	No

#### L16.2.6.1 Listing of Investigator Global Assessment (IGA)

Reference

Placebo

Test: Tazarotene Cream 0.05% (Fougera Pharmaceuticals Inc.)

Reference: TAZORAC® (tazarotene) Cream, 0.05% (Allergan, Inc.)

Placebo: Placebo (vehicle) Cream (Fougera Pharmaceuticals Inc.)

\*Treatment Success: defined as none, minimal or mild disease, a score of 0, 1 or 2 within the treatment area on the IGA at the Week 12 visit (Day  $85 \pm 4$  days, End of Study).

\*\*Treatment Success: defined as subjects with disease severity at the Week 12 visit (Day  $85 \pm 4$  days, End of Study) consistent with none or minimal, a score of 0 or 1, within the treatment area on the IGA

Path: L:\Studies\_Sas\_Codes\Clinical Trial

Created on: ddmmmyy hh:mm

4/26/2017

Page 1 of N

0453-01-01/

Protocol /

Treatment Group	Subject Number	Visit	Scaling	Erythema	Plaque Elevation	PASI Score	Clinical Success
Test	xx - xxxx	1	2	3	1	6	
		2	2	3	1	6	
		3	1	2	1	4	
		4/ET	1	1	0	2	Yes
	xx - xxxx	1	2	3	1	6	
		2	2	3	1	6	
		3	1	2	1	4	
		4/ET	1	2	0	3	No

### L16.2.6.2 Listing of Psoriasis Area Severity Index (PASI) at the Target Lesion Site

Reference

Placebo

Test: Tazarotene Cream 0.05% (Fougera Pharmaceuticals Inc.) Reference: TAZORAC® (tazarotene) Cream, 0.05% (Allergan, Inc.) Placebo: Placebo (vehicle) Cream (Fougera Pharmaceuticals Inc.)

Path: L:\Studies\_Sas\_Codes\Clinical Trial\\SAS\OUT

Created on: ddmmmyy hh:mm

Page 1 of N

0453-01-01/

Protocol /

## L16.2.6.3 Listing of Dermatological Examination

					Location	Location Target Lesion		% BSA Affected				
Treatment Group	Subject Number	Height (cm)	Weight (kg)	BSA (m^^2)	of the Target Lesion	Area (cm^^2)	V1	V2	V3	V4/ET		
Test	XX - XXXX	XXX	XXX.X	XXX.X	Head front	XXX.X	XXX.X	XXX.X	XXX.X	XXX.X		

Reference

Placebo

Test: Tazarotene Cream 0.05% (Fougera Pharmaceuticals Inc.) Reference: TAZORAC® (tazarotene) Cream, 0.05% (Allergan, Inc.) Placebo: Placebo (vehicle) Cream (Fougera Pharmaceuticals Inc.)

Path: L:\Studies\_Sas\_Codes\Clinical Trial\\SAS\OUT

Created on: ddmmmyy hh:mm

# L16.2.7.1 Listing of Adverse Events by Treatment Group

## Test: Tazarotene Cream 0.05%

	Body System/ Relationship			Relationship	Action Taken with Investigational			
Subject	MedDRA Term/	ТХ	Start /End		to Investigational		Drug /	
Number	AE Term	Area	Date	Severity	Drug	Outcome	Other Action Taken	SAE?
xx - xxxx	Nervous system disorders/ headache/	No	yyyy-mm-dd /	Mild	Not Suspected	Recovered	Drug withdrawn/ None	No
	Headache		yyyy-mm-dd					

Note to programmer: table will continue for reference and placebo group

Path: L:\Studies\_Sas\_Codes\Clinical Trial

\SAS\OUT

Created on: ddmmmyy hh:mm

Burning								
Treatment Group	Visit	Erythema	Dryness	/Stinging	Erosion	Edema	Pain	Itching
Test	1	0	0	0	1	0	0	0
	2	0	1	0	0	0	0	0
	3	0	0	0	1	0	0	0
	4/ET	0	0	0	1	0	0	2

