#### 8.4 Justification for use of Placebo

A Placebo group is included to confirm the sensitivity of the study and minimize the possibility of a false positive result of therapeutic equivalence. Therefore, in addition to demonstrating therapeutic equivalence between Test and Reference products, both active products must show statistical superiority to the Placebo.

Eligible subjects will have a 33.33% chance of being randomized to Placebo (1:1:1 randomization scheme of Test: Reference: Placebo).

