#### 8.5 Risks and Benefits

The risks and benefits to subjects enrolled in clinical research studies that include a Placebo treatment group must be carefully considered based on three main criteria, namely: the disease being treated, the availability, efficacy and safety of approved therapies, and the scientific and statistical requirements of the desired outcome of the research study. The Office of Human Rights Protection (OHRP), a Division of the United States Federal Government's Department of Health

A Multi-Center, Double-Blind, Randomized, Vehicle-Controlled, Parallel-Group Study Comparing Tazarotene Cream 0.05% to TAZORAC® (tazarotene) Cream 0.05% and Both Active Treatments to a Vehicle Control in the Treatment of Stable Plaque Psoriasis

and Human Services, has issued a detailed guidebook to IRBs that includes discussion on the use of placebos in clinical studies.

Randomized subjects will be enrolled in the study for  $85 \pm 4$  days. Although the potential for any drug-related side effects of significance occurring during the study is low, the risk is higher in the two active treatment groups than in the Placebo group. Topical application of Tazarotene can lead to drug-related effects, mainly affecting the application sites: skin itching, irritation, dryness and burning or pain sensation represent the most common side effects.

All subjects enrolled in this study will receive Investigator evaluation of their condition over 85 days. In addition, the subject will be paid for their participation, and any payments will be reviewed by the IRB and disclosed to the subject, via the informed consent form (ICF).

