## **11.2 Sample Size Determination**

Sample size calculations were performed using For the primary endpoint analysis, the rate of treatment success for the Reference treatment after 12 weeks of treatment is in the PP population. Assuming that the rates of treatment success expected to be approximately for Test and Reference treatments are the same, a sample size of subjects in each active group in the PP population will provide approximately power to demonstrate therapeutic equivalence (i.e., the 90% confidence interval (Yates' continuity-corrected) of the absolute difference between the Test and Reference rates of treatment success is within a defined equivalence range [-20% to + 20%]). The rates of treatment success for the Placebo and active treatment groups after 12 weeks of treatment are assumed to be approximately and at least respectively, in the mITT population. Using a 1:1 (active: placebo) randomization scheme, and assuming the conversion rate from mITT to PP subjects in each treatment group (Test, Reference and Placebo) of population will be about the mITT population will provide at least power to demonstrate superiority of active over Placebo at the 5% significance level (p < 0.05, two-sided continuity-corrected Z-Tests and a pooled response

rate for the standard error of the difference in proportions).

Under the above assumptions, the overall study power to demonstrate therapeutic equivalence and superiority is estimated to be at least To allow for approximately of subjects who may drop out from the study or are otherwise non-evaluable, up to 855 subjects may be randomized to obtain subjects in the mITT population (i.e., per treatment arm).

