#### 8. STATISTICAL ANALYSIS METHODS

If not otherwise specified, statistical significance is defined as p<0.05 and is two-tailed. Data will be summarized with respect to demographic and baseline characteristics, efficacy variables and safety variables.

For categorical variables, the number and percent of each category within a parameter will be

4/26/2017

■ Fougera Pharmaceuticals Inc.■

calculated for non-missing data. For continuous variables with non-missing values, statistics will include number of observations, mean, standard deviation, median, minimum and maximum values.

All statistical analyses will be conducted using SAS®, Version 9.4 or higher. Datasets will be prepared using headings from Clinical Data Interchange Consortium (CDISC) Study Data Tabulation Model (SDTM) implementation for human clinical trials and ADaM (Analysis Dataset Model).

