#### 8.3.1 Adverse Events

All the adverse events (AEs) reported throughout the study will be coded and classified according to the MedDRA (Medical Dictionary for Regulatory Activities) coding dictionary (Version 18.1 or higher). Each adverse event is to be evaluated for date of start and end, seriousness, severity, relationship to the IP, action taken and outcome.

In each of the following categories, the total number and percentage of subjects with 1) at least one AE, 2) discontinued study drug due to AEs, 3) AE severity and AEs related to the IP, 4) serious AEs and death will be summarized separately by treatment groups.

A summary table of the number and percent of subjects with AEs by system organ class, preferred term, and treatment group will be presented. Each subject will be counted only once within each preferred term.

Tazarotene Cream 0.05%	Protocol /	0453-01-01/
------------------------	------------	-------------

A frequency summary table of the number of AEs by system organ class, preferred term, severity, and treatment group will be presented. Severity will be classified as "Mild", "Moderate", or "Severe".

Similarly, a frequency summary table of the number of AEs by system organ class, preferred term, and relationship to the IP, and treatment group will be presented. Relationship to a study drug will be classified as "Suspected" or "Not Suspected".

Should sufficient data exist, adverse event frequencies will be compared between treatments using Fisher's exact test.

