#### 8.4 Multiple Comparisons

No multiple comparison adjustment will be made in this study.

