## T16.1.9.11 Summary of Frequency of All Adverse Events by Body System (Safety Population)

		Test		Reference		Placebo		
		(N =	xxx)	(N =	= xxx)	1)	N = xxx)	Fisher's
Body System	MedDRA Term	Events	Subjects	Events	Subjects	Events	Subjects	P-value
Subject with at least one AE	Total	XX	xx (xx.x%)	XX	xx (xx.x%)	XX	xx (xx.x%)	X.XXXX
Ear and labyrinth disorders	Ear pain	XX	xx (xx.x%)	XX	xx (xx.x%)	XX	xx (xx.x%)	X.XXXX
	etc.							
etc.								

Comparison of treatment groups is with respect to the number of subjects with at least one occurrence of the AE.

Test: Tazarotene Cream 0.05% (Fougera Pharmaceuticals Inc.) Reference: TAZORAC® (tazarotene) Cream, 0.05% (Allergan, Inc.) Placebo: Placebo (vehicle) Cream (Fougera Pharmaceuticals Inc.)

Path: L:\Studies_Sas_Codes\Clinical Trial\\S	SAS\OUT (	Created on: ddmmmyy hh:mm	Page 1 of N
--	-----------	---------------------------	-------------

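### The treatment-area flag in the AE listing is never summarised by arm, so the planned per-subject AE comparison is weak for local irritation; the graded site-reaction tables cover part of the gap

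*SAP*

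**What the plan says.** Protocol 8.5 describes drug effects as "mainly affecting the application sites: skin itching, irritation, dryness and burning or pain sensation represent the most common side effects". Objective 3 is to compare the safety of the three products.

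For AEs, SAP 8.3.1 states: "A summary table of the number and percent of subjects with AEs by system organ class, preferred term, and treatment group will be presented". Shell T16.1.9.11 implements this with a total row (any AE), one row per MedDRA term and one Fisher p-value column. Its footnote reads: "Comparison of treatment groups is with respect to the number of subjects with at least one occurrence of the AE". SAP 8.3.1 makes the Fisher comparison conditional on there being enough data, and SAP 8.4 adds: "No multiple comparison adjustment will be made in this study".

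Shell L16.2.7.1, "Listing of Adverse Events by Treatment Group", has a column headed TX Area; the sample headache is marked No. That column appears in no AE table from T16.1.9.10 to T16.1.9.15 and is not mentioned in SAP 8.3.1.

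Local reactions are also collected separately. Protocol 10.6.10 and Appendix C have erythema, dryness, burning/stinging, erosion, edema, pain and itching graded 0 to 3 at every visit. SAP 8.3.2 compares them between arms, with summary statistics in T16.1.9.16 and grade frequencies in T16.1.9.17.

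**The concern.** Itching, irritation, dryness, burning and pain of treated skin are separate complaints and will usually code to separate MedDRA terms. In T16.1.9.11 one tolerability signal is therefore divided among several small rows, while the total row adds every unrelated AE to it. No row counts subjects who had any AE on treated skin, although the listing already identifies those events.

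At stake is the per-subject AE evidence for Objective 3, in particular whether the Test cream irritates more than the Reference. The equivalence and superiority conclusions are not affected; they rest on the primary efficacy endpoint alone.

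**Working it through.** The documents state no AE rate and no power for safety, so there is no planned figure to reproduce. The calculation is an illustration.

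**Inputs from the documents**
- Sample size: protocol 11.2 says "up to 855 subjects may be randomized". Protocol 8.4 says "Eligible subjects will have a 33.33% chance of being randomized to Placebo", which agrees with 1:1:1. So 855 / 3 = 285 per arm.
- Level: SAP 8 says "statistical significance is defined as p<0.05 and is two-tailed".
- Test and unit: Fisher's exact test on subjects with at least one occurrence (SAP 8.3.1, T16.1.9.11).

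**Assumptions**
- Pairwise comparison of two arms.
- Local AE rate L of 16% v 8%; alternatives 12% v 6% and 20% v 10%.
- Non-local AEs in B = 15% to 25% of each arm, independent of local AEs.
- One local AE per affected subject, spread evenly over k = 4 to 6 terms.

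**Formulas**
- Pooled treatment-area row: rate L.
- Any-AE row: 1 − (1 − L)(1 − B).
- One term: L / k.
- At least one of k terms significant, treating terms as independent: 1 − (1 − t)^k, where t is the power for one term.
- Power: sum of the binomial probabilities of all tables with two-sided Fisher p at or below 0.05 in the true direction, by full enumeration.

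**Results for 16% v 8%**
- Pooled row: 81%.
- Any-AE row, B = 15%: 1 − 0.84 × 0.85 = 28.6% v 1 − 0.92 × 0.85 = 21.8%; power 43%.
- Any-AE row, B = 25%: 1 − 0.84 × 0.75 = 37.0% v 1 − 0.92 × 0.75 = 31.0%; power 29%.
- One term, k = 4: 4.0% v 2.0%; power 21%. At least one of four: 1 − (1 − 0.21)^4, about 61%.
- One term, k = 6: 2.7% v 1.3%; power 12%. At least one of six: 1 − (1 − 0.12)^6, about 55% (unrounded t used).

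**All three scenarios**

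| Local AE rate | Pooled row | Any-AE row | One pre-chosen term | At least one term |
|---|---|---|---|---|
| 12% v 6% | 67% | 19-27% | 8-14% | 40-46% |
| 16% v 8% | 81% | 29-43% | 12-21% | 55-61% |
| 20% v 10% | 91% | 43-59% | 17-28% | 66-73% |

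**Sensitivity of the one-term figure.** Even spreading lowers it. At 16% v 8%, if one term holds half of the local AEs (8% v 4%), its power is 45%. If each affected subject has two terms, it is 30-45%.

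**The graded tables for comparison.** Suppose one sign at one visit is present in 15% v 5%, with 285 per arm. The standard error is √(0.15 × 0.85/285 + 0.05 × 0.95/285) = 0.025, so the 95% interval for the 10-point difference is about 5 to 15 points. At 40% v 25% it is about 7 to 23 points. These rates are also assumed. Differences of this size would stand out in T16.1.9.17 even without a test.

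**The case against.** A reader might infer that a real difference in local irritation between arms is likely to be missed by the trial. The documents do not support that reading, and the objections to it largely stand.

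- The graded tables target this risk directly. They are neither split over MedDRA terms nor diluted by unrelated events, and they name itching, dryness, burning and pain.
- They are not mere snapshots. The procedures for Visits 2 to 4 (protocol 10.5.2 to 10.5.4) have the investigator evaluate reactions since the previous visit.
- Under protocol 10.7 the investigator decides whether a change at the application site is reported as an AE. A treatment-area AE row would therefore be less complete than the graded assessment.
- All term rows are shown without adjustment, so the power for one pre-chosen term understates the chance that something is flagged. That chance is 55-61% at 16% v 8%, not 12-21%.
- SAP 8.3.1 also plans subject counts for AEs related to the product, which removes some of the dilution.

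Three limits to these objections remain. First, the graded tables have no p-value or interval, no per-subject count of any reaction, no worst grade and no change from Visit 1. They are split by sign and visit, include erythema, which both psoriasis scales also score, and omit events outside the seven signs as well as relationship and discontinuation. Second, T16.1.9.10 places Suspected under AEs reported, and T16.1.9.14 counts events as a percentage of events, so neither clearly gives a per-subject count and neither isolates treated skin. Third, the chance of at least one significant term is still below the pooled row in every scenario, and it depends on reading several unadjusted rows.

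**Conclusion.** The point holds in a limited form. The treatment-area item is listed but never summarised by arm, and the per-subject AE comparison is therefore weak for the main known risk. At an assumed 16% v 8%, a pooled row has about 81% power, against 29-43% for the any-AE row and 55-61% for at least one unadjusted term.

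The wider conclusion that a true difference would probably go unnoticed does not follow, because the by-arm graded tables would probably reveal a large one.

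The sizes rest entirely on assumed rates, an even spread over 4-6 terms, independence between terms and pairwise Fisher tests. T16.1.9.11 shows only one p-value column for three arms, and SAP 8.3.1 runs the test only if data suffice. The direction of the comparison is more secure than the percentages. This is an inexpensive improvement to the safety reporting, not a threat to the trial's main conclusions.

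**What to change.** In SAP 8.3.1 and shells T16.1.9.10 and T16.1.9.11, add two rows by arm:

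1. Subjects with at least one AE in the treatment area (TX Area = Yes), each subject counted once.
2. The same row restricted to AEs classed as Suspected.

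Compare the arms with whatever method is used for the other AE rows. State in SAP 8.3.1 that these rows complement T16.1.9.16 and T16.1.9.17 and do not replace them, because the investigator decides which local changes become AEs.

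The cost is SAP wording and two table rows. The listing shell already shows the item, so no new data should be needed. The protocol text does not need to change.

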# L16.2.7.2 Listing of Application Site Reactions

#### Reference

Placebo

Test: Tazarotene Cream 0.05% (Fougera Pharmaceuticals Inc.) Reference: TAZORAC® (tazarotene) Cream, 0.05% (Allergan, Inc.) Placebo: Placebo (vehicle) Cream (Fougera Pharmaceuticals Inc.)

Path: L:\Studies\_Sas\_Codes\Clinical Trial

\SAS\OUT

Created on: ddmmmyy hh:mm

Page 1 of N

0453-01-01/

Protocol /

# L16.2.8.1 Listing of Pregnancy Test Results

Treatment	Subject				Visit 4 or
Group	Number	Visit 1	Visit 2	Visit 3	Early Termination
Test	XX - XXXX	Negative	Negative	Negative	Negative

